**JTA-KOA1 - Clinical Study Protocol**

JTA-KOA1-CSP	V 04	Author: EB	Date: May 10, 2017	Pg. 58/114
--------------	------	------------	--------------------	------------

[figure not shown]
## 7 SAFETY ASSESSMENTS

### 7.1 Overview of Safety Parameters and Endpoints

The safety and tolerability of investigational medicinal products will be systematically investigated throughout the whole study period. AEs will be collected and reported from the time the patient signs the informed consent until study completion. Patients will be evaluated at each visit for the potential occurrence of any AE/SAE using the following safety criteria listed in the table below. Definitions of AE and SAE are given in Section 8.1.

Table 4 below shows how the safety endpoints of this study are related to the study objectives. Assessments and measurements will be carried out at the times specified in the study Flow Chart (see Section 3.6).

*Table 4: Overview of Safety Parameters and Time Points*

#### 7.1.1 Medical History and Demographics

Medical history must be obtained at Screening. The information will be recorded on the eCRF relating to any prior or existing medical conditions/surgical procedures.

The patient will be asked to provide his/her medical history with specific dates. Those conditions reported will be compared to the inclusion and exclusion criteria for the study. Specific attention will be paid to the patient's previous history with respect to exclusionary conditions, procedures, and surgeries.

JTA-KOA1 - Clinical Study Protocol

JTA-KOA1-CSP	V 04	Author: EB	Date: May 10, 2017	Pg. 59/114
--------------	------	------------	--------------------	------------

7.1.2 Vital Signs

Vital signs [REDACTED] will be measured [REDACTED]. [REDACTED]  
[REDACTED]  
[REDACTED]  
[REDACTED]

Results of measurements should only be reported as AE if, in the Investigator’s opinion, it is outside of “expected values or variations”. They must be considered as SAE if they fulfil the SAE definition.

7.1.3 Physical Examination

[REDACTED]  
[REDACTED]  
[REDACTED]  
[REDACTED]  
[REDACTED]  
[REDACTED]  
[REDACTED]  
[REDACTED]

7.1.4 Laboratory Safety Measurements

Any sample testing will be done in line with the consent of the individual patient.

[REDACTED]  
[REDACTED]  
[REDACTED]  
[REDACTED]  
[REDACTED]

## JTA-KOA1 - Clinical Study Protocol

JTA-KOA1-CSP

V 04

Author: EB

Date: May 10, 2017

Pg. 60/114

*Table 5: Overview of Collected Volumes for Blood Analyses*

## 7.2 Other Safety Measurements

### 7.2.1 Pregnancy Test

Women with childbearing potential will undergo a urine pregnancy test at Visit #1 and #2. Pregnancy tests will be provided by the Sponsor, performed on site according to manufacturer's instructions, and results will be recorded in the eCRF.

Patients will be carefully screened to ensure that all women with childbearing potential have used a reliable method of contraception for at least 6 weeks prior to study inclusion (Screening Visit) and will use the reliable method of contraception during the whole study period. Reliable contraceptive methods include orally administered hormonal contraceptives, surgical intervention (e.g., tubal ligation), and IUD. Women who cannot comply will not be enrolled in the study. Women of non-childbearing potential must confirm that they are surgically sterile, or have been postmenopausal for at least 1 year prior to study treatment.

**JTA-KOA1 - Clinical Study Protocol**

JTA-KOA1-CSP	V 04	Author: EB	Date: May 10, 2017	Pg. 61/114
--------------	------	------------	--------------------	------------

These information will be recorded on the Medical History page of the eCRF.

### 7.2.2 Additional Safety Examinations and Procedures

If any unclear clinical event, including symptoms, signs, or other observations or abnormalities, should occur, the Investigator, or any other physician in charge, may perform additional clinical examinations and procedures (other than outlined in this protocol), including any clinical, laboratory, imaging and/or technical testing, in order to clarify and establish the aetiology and diagnosis of this clinical event.

**JTA-KOA1 - Clinical Study Protocol**

JTA-KOA1-CSP

V 04

Author: EB

Date: May 10, 2017

Pg. 62/114

**8 SAFETY DEFINITIONS AND REPORTING REQUIREMENTS****8.1 Definitions****8.1.1 Adverse Event (AE)**

An adverse event (AE) is defined as any untoward medical occurrence in a patient or clinical investigation subject who has been administered a pharmaceutical product and/or any investigational medicinal product and which does not necessarily have a causal relationship with this treatment. An AE can therefore be any unfavourable and unintended signs (including any abnormal laboratory findings), symptoms, or disease temporally associated with the use of a medicinal product, without any judgment about causality. Adverse events will be graded with respect to intensity and classified as either serious or non-serious according to the World Health Organisation Classification.

All disease signs and symptoms experienced by the patient will be recorded on the eCRF from the time of the patient signs the ICF until completion of the final study visit.

If clinically significant worsening of the patients' physical condition is noted, the changes will be documented as AE on the AE Page of the eCRF. Clinical significance is defined as any variation in signs, symptoms, or testing that has medical relevance and may result in an alteration in medical care.

**8.1.2 Serious Adverse Event (SAE)**

An SAE is defined as any AE or SAR that, in the view of the investigator or sponsor, results in any of the following outcomes (ICH E2a):

- Death
- Life-threatening AE
- Inpatient hospitalization or prolongation of existing hospitalization
- Persistent or significant incapacity or substantial disruption of the ability to conduct normal life functions
- Congenital anomaly/birth defect

JTA-KOA1 - Clinical Study Protocol				
JTA-KOA1-CSP	V 04	Author: EB	Date: May 10, 2017	Pg. 63/114

Medical and scientific judgement should be exercised in deciding whether expedited reporting is appropriate in other situations, such as important medical events that may not be immediately life-threatening or result in death or hospitalisation but may jeopardise the patient or may require intervention to prevent one of the other outcomes listed in the definition above.

**Notes**

Life-threatening means that the patient is at immediate risk of death at the time of the event; it does not refer to an event, which hypothetically might have caused death if it was more severe or had continued untreated. The term "life-threatening" does not imply a possible future course which might or might not have happened, but was prevented due to adequate physician's action. For example, a simple bacterial wound infection can potentially lead to gangrene, sepsis, and eventually death; while sepsis is usually regarded as a SAE because of known high mortality, the primary wound infection itself is usually not regarded as a SAE. In analogy, a newly diagnosed malignant disease is usually regarded as a SAE because malignant diseases usually have a high mortality rate and are therefore life-threatening.

Planned hospitalization for a pre-existing condition, or a procedure required by the protocol, without serious deterioration in health, is not considered a serious adverse event.

Congenital anomaly means any physiological or physical defect observed in a child born from a mother who participated in the current study and who became pregnant during the course of this study.

## JTA-KOA1 - Clinical Study Protocol

JTA-KOA1-CSP

V 04

Author: EB

Date: May 10, 2017

Pg. 64/114

### 8.1.3 Severity and Seriousness

AEs will be graded with respect to their severity and seriousness according to the World Health Organisation Classification.

**Table 6: Classification of Adverse Events**

Severity	Mild	Some awareness of symptoms or signs that does not interfere with the patient's usual activities or is transient, easily tolerated and resolved without treatment and with no sequelae
	Moderate	Symptoms or signs causing enough discomfort to interfere with the patient's usual activities, and/or requires symptomatic treatment
	Severe	Incapacitating event, including symptoms or signs, causing severe discomfort and inability to work or to perform usual activities, and requires treatment
Seriousness	Serious (SAE)	Any adverse event that led to: 
 
– death,
 
– serious deterioration in health of the patient, that either resulted in               
 
1. a life-threatening illness or injury, or
 
2. a permanent impairment of a body structure or a body function, or
 
3. in-patient or prolonged hospitalisation, or
 
4. medical or surgical intervention to prevent life-threatening illness or injury or permanent impairment to a body structure or a body function,
 
 
 
– foetal distress, foetal death or a congenital abnormality or birth defect
 

	Non-serious	Any other adverse event

To avoid confusion or misunderstanding of the difference between the terms "serious" and "severe", which are not synonymous, the following clarification is provided: the term "severe" is often used to describe the severity (intensity) of a specific event (as in mild, moderate, or severe myocardial infarction); the event itself however may be of relatively minor medical significance (such as severe headache). This is not the same as "serious," which is based on patient/event outcome or action criteria usually associated with events that pose a threat to the patient's life or functioning.

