## JTA- KOA1 - Clinical Study Protocol

JTA-KOA1-CSP	V 04	Author: EB	Date: May 10, 2017	Pg. 21/114
--------------	------	------------	--------------------	------------

- **Patient:** an individual who participates in a clinical trial, either as a recipient of the investigational medicinal product or a member of the reference group
- **Randomisation:** process of assigning patients to the investigational medicinal product or reference groups using an established recognized statistical methodology to determine the assignment in order to reduce bias
- **Reference (treatment):** an investigational or marketed product (e.g., active control), placebo, used in the reference in a clinical trial
- **Screened patient:** patient who has dated and signed the informed consent form (enrolled patient) and who has performed the checking of the selection criteria
- **Screening failure:** screened patient but who is not eligible for the study after checking the selection criteria
- **Serious Adverse Event (SAE):** any untoward medical occurrence or effect in a patient or clinical trial patient administered a medicinal product, which does not necessarily have a causal relationship with this treatment, and that, at any dose, results in death, is life-threatening, requires patient hospitalization or prolongation of existing hospitalization, results in persistent or significant disability or incapacity, or is a congenital anomaly or birth defect.
- **Serious Adverse Reaction (SAR):** any untoward and unintended responses to an investigational medicinal product related to any dose administered (having a reasonable causal relationship to the product), and that results in death, is life-threatening, requires patient hospitalization or prolongation of existing hospitalization, results in persistent or significant disability or incapacity, or is a congenital anomaly or birth defect.
- **Source data:** all information in original records, certified copies of original records of clinical findings, observations, or other activities in a clinical trial, necessary for the reconstruction and evaluation of the trial
- **Source document:** printed, optical or electronic document containing source data
- **Sponsor:** individual, company, institution or organization which takes responsibility for the initiation, management and/or financing of a clinical trial

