#### 8.1.4 Causal Relationship towards the Investigational Medicinal Product

In practice, determination of the causal relationship between an AE and the investigational medicinal product must be made by the Investigator by answering the following questions:

“Do you consider that there is a reasonable possibility that the event may have been caused by the investigational medicinal product?”

according to the following definitions:

- Yes: the relationship of the AE and the use of the product can be definitely established.
- Possible: there is no clear relationship between the AE and the use of the study product; however, one cannot definitely conclude that there is no relationship.
- No: there is no relationship between the AE and the use of the investigational medicinal product. This may include but is not limited to the incident being an expected outcome of a previously existing or concurrent disease, concomitant medication or procedure the patient experienced.
- Unknown: the relationship of the AE and the use of the product is not assessable

The causality assessment given by the Investigator should not be downgraded by the Sponsor. If the Sponsor disagrees with the Investigator’s causality assessment, both, the opinion of the Investigator and the Sponsor should be provided with the report.

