**JTA-KOAI - Clinical Study Protocol**

JTA-KOAI-CSP

V 04

Author: EB

Date: May 10, 2017

Pg. 69/114

All reportable events must be notified by the Investigator to the Study Safety Officer (SSO).

SAEs will be documented on the SAE Report containing a detailed written description of the event.

SAE Reports Forms should be completed, signed and sent by the Investigator not later than

**within 24 hours of event occurrence or awareness** to the SSO by e-mail [REDACTED]

[REDACTED] who will inform the Sponsor of the safety event occurrence.

Briefly, the SAE Report Form will include the following information and differentiated assessment:

- Patient Identification Number
- Investigation site and country
- Event: organ system
- SAE status and description
- Date of event onset and event resolution
- Outcome (recovery with or without sequelae, ongoing, death)
- Action taken (none, patient discontinuation and withdrawal from the study, change in concomitant medication(s) and/or new medication(s), inpatient hospitalisation or prolongation of existing inpatient hospitalisation, non-drug therapy given, other)
- Criteria for seriousness (death, life-threatening, medical or surgical intervention to prevent life-threatening illness or injury or permanent impairment to a body structure, permanent impairment of a body structure or a body function, new or prolonged hospitalisation, congenital abnormality or birth defect), and severity (mild, moderate, severe)
- Assessment of relationship to the investigational medicinal product (evaluated as yes, possibly, no)
- Assessment of relationship to procedures, including the treatment injection and blood sampling (evaluated as yes, possibly, no)

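### The protocol carries conflicting lists of what makes an adverse event serious: incapacity that is not permanent is serious under Section 8.1.2 but non-serious under Table 6

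*Combined protocol and SAP*

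**What the plan says.** **Seriousness.** Section 8.1.2, which refers to ICH E2a, includes among its serious outcomes "Persistent or significant incapacity or substantial disruption of the ability to conduct normal life functions". The SAE entry in the Definitions of Terms and the serious adverse reaction definition in Section 8.1.7 both include an event that "results in persistent or significant disability or incapacity". None of the three requires permanence.

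Section 8.1.3 says that seriousness is graded by the WHO classification, and Table 6 sets out the categories. Its closest item is "a permanent impairment of a body structure or a body function". Table 6 also makes preventive medical or surgical intervention, foetal distress and foetal death serious. Its non-serious row reads "Any other adverse event".

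Section 8.4.1 summarises the SAE report form as carrying "Criteria for seriousness (death, life-threatening, medical or surgical intervention to prevent life-threatening illness or injury or permanent impairment to a body structure", followed by "permanent impairment of a body structure or a body function, new or prolonged hospitalisation, congenital abnormality or birth defect".

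**Causality.** Section 8.1.4 defines four answers: yes, possible, no and a fourth, "Unknown: the relationship of the AE and the use of the product is not assessable". The form summary in Section 8.4.1 has "Assessment of relationship to the investigational medicinal product (evaluated as yes, possibly, no".

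**The concern.** The lists could be taken for wording variants of one definition, but their content differs. Permanent impairment is narrower than persistent or significant incapacity, and the residual row of Table 6 turns the omission into a positive classification as non-serious. No section says which list governs, and the two sections cite different sources.

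Seriousness decides whether the 24-hour notification in Section 8.4.1 applies and whether an event enters the SAE counts that Section 10.7.7 compares between groups. Section 2.3 says that JTA-004 has not yet been given to humans, and most of the local events foreseen in Table 8 concern the joint itself. A temporary but marked loss of knee function is thus a realistic event to have to classify.

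The causality scale feeds two further places: the tabulation by relationship in Section 10.7.7, and the stopping rule in Section 8.4.3, which is worded around SAEs thought to be possibly related.

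**Working it through.** There is no figure in the plan to reproduce. The check is an item-by-item comparison of the lists.

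| Criterion | Definitions and 8.1.7 | 8.1.2 | Table 6 | Form summary, 8.4.1 |
|---|---|---|---|---|
| Death | yes | yes | yes | yes |
| Life-threatening | yes | yes | yes | yes |
| Hospitalisation, new or prolonged | yes | yes | yes | yes |
| Persistent or significant incapacity | yes | yes | **no** | **no** |
| Permanent impairment | not separately | not separately | yes | yes |
| Preventive intervention | no | judgement on expedited reporting only | yes | yes |
| Congenital anomaly | yes | yes | yes | yes |
| Foetal distress or foetal death | no | no | yes | no |

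Three hypothetical events, taken through the lists:

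1. *A patient is significantly incapacitated for some weeks and then recovers, with no admission, threat to life or preventive intervention.* Serious under Section 8.1.2 and the Definitions. Under Table 6 it meets no listed criterion and falls into the non-serious row. The form summary has no criterion to tick. Incapacity does appear in Table 6, but only as a description of severe intensity, and the note below the table warns that severe and serious are different things. A reader working from the table would record the event as severe and non-serious.
2. *An outpatient intervention prevents permanent impairment, with no incapacity.* Serious outright under Table 6. It is not a listed outcome in Section 8.1.2, which leaves expedited reporting of such events to judgement.
3. *Foetal distress with a normal birth.* Serious under Table 6 and not listed in Section 8.1.2. In practice Section 8.5.1 already handles any pregnancy as an SAE, so this difference matters little.

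The first case can lose an SAE; the second can add one.

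**Causality.** Section 8.1.4 has four categories and the form summary three, so the unknown category has no counterpart. Section 8.4.1 makes every SAE reportable, and Section 8.4.2 has the safety officer forward SAEs to ethics committees and agencies with no condition on relatedness. The missing answer therefore does not stop a notification. It leaves open whether an SAE of unknown causality counts as related in the Section 10.7.7 tables, and whether it meets the possibly related condition in Section 8.4.3.

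**The case against.** The uncovered event is narrow: it must be incapacitating, not permanent, not life-threatening, and involve neither admission nor preventive intervention. For that event, three places in the protocol call it serious against one residual row, and the note under Table 6 itself links seriousness to threats to life or functioning. The form is completed after an event has been judged serious, so its summary cannot by itself make the event non-serious. Section 8.4.4 also has the sponsor receive listings of all AEs, so a misgraded event would still be visible there. These points limit the consequences, but they do not remove the contradiction. An investigator who follows the table as printed reaches a different answer from one who follows Section 8.1.2.

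The form is described only briefly in Section 8.4.1, and the form itself is not among the documents. It may hold more items. That caveat applies to the form and not to Table 6.

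On causality, the definition of a possible relationship in Section 8.1.4 covers cases where a relationship cannot be definitely excluded. Unassessable events could reasonably be placed there. The protocol does not say so, and it defines unknown as a separate category.

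A reader might infer that an SAE of unassessable causality would go unreported. Sections 8.4.1 and 8.4.2 rule that out. A reader might also fault Table 6 for lacking the unknown category, but the table covers only severity and seriousness, so the mismatch lies between Sections 8.1.4 and 8.4.1.

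**Conclusion.** The seriousness conflict stands. Table 6 as written classes as non-serious an event that Sections 8.1.2 and 8.1.7 and the Definitions treat as a serious outcome, and it adds items that Section 8.1.2 does not list as outcomes. The causality mismatch also stands, as a minor recording point.

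The effect is on the 24-hour notification, the SAE counts and the related-event tables. It does not reach the primary efficacy analysis or the sample size. The stopping rule in Section 8.4.3 is touched only through its wording on relatedness. It is discretionary and uses no SAE rate.

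The size cannot be stated, because the documents give no expected frequency for such events. A reader might take 1/41 = 2.4 percentage points as the size, from the planned 41 patients per group. That is the weight of any single patient in a group of 41 and does not say how many events would be reclassified. The 41 also includes an allowance for 10% drop-out, whereas safety is analysed in all treated patients. The conclusion rests on the protocol text alone and does not depend on what the actual form contains.

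**What to change.** Reconcile Section 8.1.2, Table 6 and the form description in Section 8.4.1 to one seriousness list. It should contain every Section 8.1.2 criterion and state explicitly whether the additional Table 6 items (preventive intervention, foetal distress, foetal death) are kept. Say which classification governs.

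Use one causality scale in Sections 8.1.4 and 8.4.1. State in Section 10.7.7 how an unknown relationship is counted in the related-event tables, and in Section 8.4.3 whether it falls within possibly related.

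The cost is protocol wording, plus an update of the SAE form if it proves to match its summary. No design, sample size or efficacy analysis changes.

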**JTA-KOA1 - Clinical Study Protocol**

JTA-KOA1-CSP

V 04

Author: EB

Date: May 10, 2017

Pg. 65/114

#### 8.1.4 Causal Relationship towards the Investigational Medicinal Product

In practice, determination of the causal relationship between an AE and the investigational medicinal product must be made by the Investigator by answering the following questions:

“Do you consider that there is a reasonable possibility that the event may have been caused by the investigational medicinal product?”

according to the following definitions:

- Yes: the relationship of the AE and the use of the product can be definitely established.
- Possible: there is no clear relationship between the AE and the use of the study product; however, one cannot definitely conclude that there is no relationship.
- No: there is no relationship between the AE and the use of the investigational medicinal product. This may include but is not limited to the incident being an expected outcome of a previously existing or concurrent disease, concomitant medication or procedure the patient experienced.
- Unknown: the relationship of the AE and the use of the product is not assessable

The causality assessment given by the Investigator should not be downgraded by the Sponsor. If the Sponsor disagrees with the Investigator’s causality assessment, both, the opinion of the Investigator and the Sponsor should be provided with the report.

